2.4.3. TERTIARY (EXPLORATORY) OUTCOMES

The following outcomes will be analysed as described in section 1.7.2:

- Change in biomarkers of LV remodelling: sST2, Galectin 3, TIMP-1, MMP-9, Type III Procollagen Peptide, GDF-15 and other relevant biomarkers of interest.
- Change in neurohormonal levels: BNP, MR-proANP, C-terminal ANP, CNP, MR-proADM, cGMP, endothelin-1, neprilysin antigen, renin and aldosterone and other relevant biomarkers of interest.
- Change in extracellular volume (ECV), left ventricular global function index (LVGFI), T1 relaxation time and left ventricular strain as measured using cardiac MRI.

2.4.4. SUBGROUP ANALYSIS

Due to the impact of the Covid-19 pandemic on the scheduling of end-of-study MRI scans, all efficacy outcomes outlined in Section 2.4 will be analysed in three subgroups of the randomised population determined by whether the patient had their 12-month MRI scan earlier than planned, on-time or later than planned. A scan will be defined as: on-time if it occurs within a 7-day window around the scheduled 52-week visit date; early if more than 7 days prior; and late if more than 7 days following the scheduled visit date.

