1.5. SAMPLE SIZE AND POWER

Section 11.1 of the study protocol states:

"A sample size of 100 patients is proposed. This is based on the calculation that 45 patients per treatment group provides >90% power (α level = 0.05) to detect a difference of 6mL/m² in LVESVI (standard deviation = 7.8mL/m²) and accounting for a discontinuation rate of 10% (lost to follow up, development of heart failure or death). A 6mL/m² difference in LVESVI represents a minimally important difference."

Recruitment of 100 patients in 18 months requires a monthly recruitment rate of 5.6 patients/month or 1.4 patients/week.

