1.7.2. GENERAL PRINCIPLES

Data will be summarised for all participants and by randomised treatment group where appropriate. Categorical variables will be summarised with the number of observations and missing values, and number and percentage of participants falling into each category. Continuous variables will be summarised using the number of observations and number missing, mean, standard deviation (SD), median, 25th and 75th quartiles (Q1 and Q3 respectively), minimum and maximum values. Rates of recruitment and retention will be summarised as counts and percentages with 95% confidence intervals.

All efficacy outcomes will be analysed using regression analysis models that are adjusted for the baseline value of the outcome in question and whether or not taking diuretics at baseline. Efficacy outcomes will be summarised at baseline, 12 months and for the change from baseline at 12 months, presented overall and by treatment group. The model's intervention group treatment effect (and 95% CI) and p-value will be presented for outcome results measured at 12 months. All biomarker outcomes will additionally be summarised at 6 months and for the change from baseline at 6 months. Furthermore, a repeated measures linear regression model will be performed for each biomarker outcome, adjusting for the main effects of time-point and randomised group and the interaction between time-point and randomised group. The intervention group

treatment effect and time-point effect (and 95% CIs) will be presented with p-values for these main effects and their interaction.

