2.4. EFFICACY OUTCOMES

2.4.1. PRIMARY OUTCOME

The change in indexed left ventricular end-systolic volume (LVESVI) from baseline to the 12 month follow-up visit will be summarised overall and by randomised group and compared between randomised groups using a linear regression model adjusted for baseline LVESVI, diuretic use at baseline and time from baseline to the 12 month follow-up visit.

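### SAP 2.4.4 analyses every efficacy outcome within early, on-time and late scan subgroups but plans no treatment-by-scan-timing interaction, so it cannot show whether shifted scans changed the treatment effect

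*SAP*

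**What the plan says.** SAP 2.4.4 cites the effect of the pandemic on end-of-study MRI scheduling and then states that "all efficacy outcomes outlined in Section 2.4 will be analysed in three subgroups of the randomised population". A scan is on time if it falls within a 7-day window around the scheduled week-52 date. It is early or late if it is more than 7 days off.

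SAP 1.7.2 sets the reporting for efficacy models: the "intervention group treatment effect (and 95% CI) and p-value will be presented for outcome results measured at 12 months". SAP 2.4.4 names no other form of output, so the natural reading is an estimate, interval and p-value in each subgroup.

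Two other places touch on time:
- SAP 2.4.1 has the LVESVI model "adjusted for baseline LVESVI, diuretic use at baseline and time from baseline to the 12 month follow-up visit". Time enters there as a main effect only.
- SAP 1.7.2 has a time-point by randomised-group interaction, but only in the repeated-measures biomarker models, where time-point means the scheduled visit.

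Protocol 11.3 plans no subgroup analysis, so SAP 2.4.4 is the only specification of this work.

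**The concern.** The useful question about displaced scans is whether the treatment effect depends on when the scan was done. That is a comparison between subgroups. A test of treatment within each subgroup is a different thing: whether it crosses 0.05 depends heavily on how many patients are in the subgroup. The main-effect time covariate in SAP 2.4.1 adjusts for timing but assumes the same treatment effect at every scan time. The visit-by-group interaction in SAP 1.7.2 concerns another variable.

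As written, the report could show a significant effect among on-time scans and a non-significant one among late scans. It would give the reader no means of telling a real timing effect from chance. Such a pattern could be taken to mean that the pandemic diluted the result, or that only on-schedule scans can be trusted.

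The cut-points add a smaller difficulty. With a ±3-month visit window (Protocol 8.4), a scan 8 days late shares a category with one about 3 months late.

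**Working it through.** **Inputs (SAP 1.5, quoting Protocol 11.1).** "45 patients per treatment group provides >90% power" "to detect a difference of 6mL/m² in LVESVI", with "standard deviation = 7.8mL/m²" and "α level = 0.05". Sidedness is not stated; two-sided is assumed.

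**Inputs not in the documents.** Subgroup sizes. Four splits of the 45 per arm were assumed, as early/on-time/late: 15/15/15, 5/20/20, 5/30/10 and 8/12/25. Whatever the split, the smallest of three groups among 90 patients has at most 30.

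**1. The plan's own figure.** Power is the probability that a noncentral t, with 2n − 2 df and noncentrality δ/(σ√(2/n)), exceeds the two-sided 5% critical value. With n = 45, δ = 6 and σ = 7.8, power is 95.0%, which agrees with the stated figure. The total of 90/0.9 = 100 also agrees.

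**2. Within one subgroup.** With 15 per arm, SE = 7.8 × √(2/15) = 2.85 mL/m². The 95% CI half-width is 2.048 × 2.85 = 5.8 mL/m², nearly the whole target difference, and power is 53%. With 5 per arm the half-width is 11.4 mL/m² and power is 19%.

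**3. Mixed significance under one common effect of 6 mL/m².** The subgroups are independent, so P(mixed) = 1 − p₁p₂p₃ − (1 − p₁)(1 − p₂)(1 − p₃).

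| Split per arm | Power in each | All three significant | Mixed |
|---|---|---|---|
| 15/15/15 | 0.530, 0.530, 0.530 | 0.149 | 0.747 |
| 5/20/20 | 0.189, 0.659, 0.659 | 0.082 | 0.824 |
| 5/30/10 | 0.189, 0.834, 0.370 | 0.058 | 0.857 |
| 8/12/25 | 0.300, 0.437, 0.760 | 0.100 | 0.806 |

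For the first row: 1 − 0.530³ − 0.470³ = 1 − 0.149 − 0.104 = 0.747. In simulation, the three estimates differ by 4.8–6.1 mL/m² on average through chance alone, and by 6 or more in 30–46% of trials.

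**4. Dependence on the true effect and the SD.** SD 5.5 is an assumption, to show what baseline adjustment might do. Ranges are over the four splits.

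| Common true effect (mL/m²) | Mixed, SD 7.8 | Mixed, SD 5.5 |
|---|---|---|
| 6 | 75–86% | 44–79% |
| 3 | 43–45% | 63–67% |
| 2 | 28% | 40–42% |
| 0 | 14% | 14% |

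The last row is 1 − 0.05³ − 0.95³ = 0.1425. A smaller SD lowers the chance of a mixed result at an effect of 6 but raises it at 3 and 2.

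**5. What an interaction test would do.** With no true difference between subgroups, a 2-df F test (84 denominator df) gives a false timing effect in 5% of trials per outcome. Its power depends on λ = Σwᵢ(δᵢ − δ̄)², with wᵢ = nᵢ/(2σ²) and δ̄ the weighted mean. For equal thirds and effects 0/6/6: w = 15/(2 × 60.84) = 0.1233, δ̄ = 4, λ = 0.1233 × (16 + 4 + 4) = 2.96, power 31%. Over the four splits, with any one subgroup at zero and the others at 6, power is 16–34%.

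**6. Volume.** SAP 2.4.1–2.4.3 names 1 + 7 + 20 = 28 outcomes (strain counted once), so 28 × 3 = 84 subgroup comparisons.

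**The case against.** The strongest reply is that SAP 2.4.4 never claims to test whether timing alters the effect. It may only be meant to display results, for instance among patients scanned on schedule, and it does not itself mention p-values. Both statements are accurate: the p-values come from reading it with SAP 1.7.2. But if the aim is descriptive, the SAP should say so and leave the p-values out.

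A reader might also infer more than the documents support:
- **That mixed results are certain, or usual.** The 75–86% needs a true effect of 6 mL/m² with SD 7.8. At an effect of 3 it is below one half with that SD. The calculation uses unadjusted t-tests and assumed subgroup sizes, whereas the plan uses adjusted regression.
- **That the primary result is compromised.** It is not. The primary model uses the whole randomised population and already adjusts for time to the visit.
- **That 84 comparisons measure the harm.** Of the 28 outcomes, 20 are labelled exploratory.
- **That the subgroup models cannot be fitted.** A time covariate with little spread in the on-time group is a minor matter and applies only to LVESVI, since SAP 1.7.2 has no such term for the other outcomes. Even 10 patients leave 5 residual df after an intercept and four regressors: imprecise, but normally estimable.

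It is also fair to say that an interaction test here is weak and could be misread as showing that timing did not matter. That stands, and the fix must deal with it.

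**Conclusion.** The omission is real. No section of the SAP or protocol plans a treatment-by-scan-timing interaction, and separate subgroup p-values cannot stand in for one. Under the plan's 90 evaluable patients and SD 7.8, a constant effect would give a mixed pattern of significance in anywhere from 28% (effect 2 mL/m²) to 86% (effect 6, least favourable assumed split) of trials. With no effect the figure is 14%. These figures rest on assumed subgroup sizes and unadjusted tests, and they apply to LVESVI only.

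Scan timing is also known only after randomisation, so its categories are not baseline subgroups. Protocol 6.5 asks patients who withdraw, or who start open-label sacubitril/valsartan, at 6 months or later to have an end-of-study CMR. If such a scan counts as the 12-month scan, which the SAP does not settle, the early group would mix these patients with pandemic rescheduling.

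The consequence is limited to how timing is interpreted, but that is the evident reason for SAP 2.4.4. The change should be made.

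**What to change.** In SAP 2.4.4, for each outcome:

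1. Replace the three separate fits by one model on all patients with that outcome and a classifiable scan date. Include randomised group, the planned covariates, the three-level timing category and its interaction with group.
2. Report the 2-df interaction test, and from the same model the early, on-time and late effects with 95% CIs and patient numbers. Give no subgroup p-values.
3. As a supporting model, use continuous time from baseline to scan and its interaction with group. For LVESVI, use the time term already in SAP 2.4.1: if the scan is done at the visit, weeks from week 52 is that variable less a constant and must not be added beside it. For the other outcomes, add time as a main effect as well. This model does not itself yield the three category effects, which is why the categorical model is needed.
4. State that the analysis is exploratory, that timing is a post-randomisation variable, and that the interaction test has low power (about 16–34% under the assumed splits when one subgroup has no effect and the others have 6 mL/m²). A non-significant result therefore does not show that timing had no influence.

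The cost is SAP wording and one or two extra model terms per outcome. No new data are needed, there are fewer p-values to report and the primary analysis does not change. The drawback is a test with low power.

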2.5. SAFETY OUTCOMES

2.5.1. PREMATURE WITHDRAWAL

The number and percentage of subjects who complete the intervention phase will be reported. The number and percentage of subjects who actively withdraw from study medication and/or the study will be reported and the reasons for withdrawal will be summarised if provided.

2.5.2. ADVERSE EVENTS OF INTEREST

Adverse events of interest include:

- Worsening renal function or acute kidney injury
- Hyperkalaemia
- Symptomatic hypotension
- Symptomatic hypotension with systolic BP <90mmHg
- Angioedema
- Cough

The number and percentage of subjects experiencing one of the adverse events of interest listed will be summarised overall and by randomised treatment group. The Fisher's Exact test will be used to assess whether there is a statistical difference between number of subjects experiencing each event between treatment groups. The following event details will also be summarised and compared between groups: seriousness criteria, severity, relationship to study drug and details of action taken. Full details of these events are provided in section 10.2 of the study protocol.

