6.8 Monitoring of potential side effects

6.8.1 Management of nephrotoxicity

Both study drugs are potentially nephrotoxic and close monitoring of renal function (serum urea, creatinine and electrolytes) for the duration of the trial will be mandatory. This will include baseline measurements along with measurements prior to and after the introduction of the study drug and after any dose change. Measurements will also be taken at regular intervals for the duration of the trial. Alert ranges for laboratory and other test abnormalities are included in Appendix 1. Additional measurements will be used if clinically indicated. All results will be reviewed in a timely manner when available and if action is required this will be expedited immediately. Each patient will have their renal function (along liver function tests) checked at the following time-points:

- Visit 1: Week 0 (pre-randomisation)
- Visit 2: Week 1 (± 3 days)
- Visit 3: Week 2 (± 3 days)
- Visit 4: Week 4 (± 3 days - pre up-titration of study drug)
- Visit 5: Week 5 (± 3 days - 1 week post up-titration of study drug)
- Visit 6: Week 14 (± 7 days)
- Visit 7: Week 26 (± 7 days)
- Visit 8: Week 39 (± 7 days)
- Visit 9: Week 52 (± 7 days)

If, at any time after randomisation, eGFR decreases by $\geq 25\%$ from baseline (or if serum creatinine concentration increases to $221\text{ }\mu\text{mol/L}$), potentially reversible cases of renal dysfunction will be sought including: non-steroidal anti-inflammatory drug

intake, antibiotics, or other nephrotoxic medications; hypovolaemia; and urinary tract infection. If felt to be appropriate, the study drug dose can be reduced and continued with regular monitoring of renal function. If a patient's eGFR decreases by $\geq 40\%$ from baseline (or if serum creatinine concentration rises above 265 $\mu\text{mol/L}$, then this is an indication to stop the study drug. Thereafter, serum creatinine assessments will have to be repeated at least weekly until levels return to acceptable values. Re-challenging with the study drug at a lower dose level will be considered if deemed clinically safe to do so.

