6.8.2 Management of hyperkalaemia

Patients with elevated potassium value will be managed according to the corrective actions outlined below.

Serum potassium > 5.3 and less than or equal to 5.5 mmol/L

- Confirm potassium concentration in a non-haemolysed sample
- Reinforce low potassium diet and restriction of food/drinks with high potassium content
 - (e.g. orange juice, melon, bananas, low-salt substitutes etc.)
- Review medical regimen (including dietary supplements and over-the-counter medications) for agents known to cause hyperkalaemia. Consider reduction in dose or discontinuation of these agents:
 - Potassium-sparing diuretics (e.g. amiloride and triamterene) including in combination products with thiazide or loop diuretics
 - Potassium supplements, e.g., potassium chloride
 - Salt substitutes
 - Non-steroidal anti-inflammatory drugs (NSAIDs)
 - Cyclo-oxygenase-2 (COX-2) inhibitors
 - Trimethoprim and trimethoprim-containing combination products
 - Herbal Supplements: For example, Noni juice, alfalfa (*Medicago sativa*), dandelion (*Taraxacum officinale*), horsetail (*Equisetum arvense*), nettle (*Urtica dioica*), milkweed, lily of the valley, Siberian ginseng, hawthorn berries
- Repeat serum potassium measurement within 3 to 5 days
- If serum potassium remains > 5.3 and ≤ 5.5 mmol/L, regularly monitor serum potassium levels to ensure stability (suggested once monthly)
- Consider down-titration of study medication, according to investigator's medical judgment.

Serum potassium > 5.5 and < 6.0 mmol/L

- Confirm potassium concentration in a non-haemolysed sample
- Consider down-titration or temporarily discontinue study drug according to investigator medical judgment.
- Apply all measures outlined for serum potassium > 5.3 and ≤ 5.5 mmol/L
- Repeat serum potassium measurement after 2-3 days
- If serum potassium < 5.5 mmol/L, consider resumption of study drug at lower dose with repeat potassium within 5 days

Serum potassium greater than or equal to 6.0 mmol/L

- Immediately discontinue study drug

- Confirm potassium concentration in a non-haemolysed sample
- Urgently evaluate patient and treat hyperkalaemia as clinically indicated
- Apply all measures outlined for serum potassium > 5.3 and < 6.0 mmol/L
- Resumption of study drug will be decided on a case-by-case basis by the investigators.

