10.2 Recording and reporting of Adverse Events

All AEs occurring during the trial that are observed by the Investigator or reported by the participant should be recorded in the participant's medical records whether or not attributed to trial medication.

Details of the following adverse reactions will be collected within the eCRF at all follow up visits from randomisation until the participants' final visit.

- Clinically relevant hypotension (syncope, dizziness, etc)
- Worsening renal function
- Acute kidney injury
- Hyperkalaemia
- Occurrence of angioedema

The seriousness of each adverse reaction will be collected along with the outcome of the event at the time of the visit i.e. whether the reaction is ongoing at the time of the visit or the participant has recovered.

SAEs will be documented within the eCRF and will be collected from the date of randomisation until 30 days post cessation of trial treatment to allow for reporting of any ongoing adverse reactions associated with the use of the trial drug.

The following events are excluded from the need for expedited reporting:

- Routine treatment or monitoring of the studied indication not associated with any deterioration in condition.
- Treatment which was elective or pre-planned, for a pre-existing condition not associated with any deterioration in condition, e.g. pre-planned hip replacement operation which does not lead to further complications.
- Any admission to hospital or other institution for general care where there was no deterioration in condition.
- Treatment on an emergency, outpatient basis for an event not fulfilling any of the definitions of serious as given above and not resulting in hospital admission.

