Appendix 1: Clinically notable laboratory values

Clinically notable laboratory abnormalities for selected tests based on a percent change from baseline:

Haematology

Hematocrit >50% increase, >20% decrease
Haemoglobin >50% increase, >20% decrease
Platelet count >75% increase, >50% decrease
RBC Count >50% increase, >20% decrease
WBC count >50% increase, >50% decrease

Biochemistry

Alkaline phosphatase >100% increase
ALT >150% increase
AST >150% increase
BUN >50% increase
Chloride >10% increase, >10% decrease
Creatinine >50% increase
Potassium >20% increase, >20% decrease
Total bilirubin >100% increase

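### Hyperkalaemia and renal worsening are compared only as reported events without a numeric definition, and no post-baseline analysis of potassium, creatinine, eGFR or SBP is specified

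*SAP*

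**What the plan says.** SAP 2.5.2 lists the adverse events of interest, among them hyperkalaemia and worsening renal function or acute kidney injury (AKI). It says: "The number and percentage of subjects experiencing one of the adverse events of interest listed will be summarised overall" and by treatment group. It then adds: "The Fisher's Exact test will be used to assess whether there is a statistical difference between number of subjects experiencing each event between treatment groups". For definitions it offers one pointer: "Full details of these events are provided in section 10.2 of the study protocol".

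Protocol 10.2 introduces its list as follows: "Details of the following adverse reactions will be collected within the eCRF at all follow up visits from randomisation until the participants' final visit". The list consists of names. The general recording rule in the same section is: "All AEs occurring during the trial that are observed by the Investigator or reported by the participant should be recorded" in the medical records.

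Protocol 6.8.1 and Table 9-1 schedule renal function and electrolytes at Visit 1 and at Visits 2 to 9. Table 9-1 schedules blood pressure at the same visits. SAP 2.3 lists creatinine, potassium, eGFR and SBP as baseline characteristics.

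**The concern.** The SAP attaches a p-value to an event that neither document defines numerically. Whether a raised potassium or a fall in eGFR counts depends on someone recording it as hyperkalaemia or renal worsening, although measured values are scheduled at every visit. A value that crosses a limit but is not reported as an event would not appear in any planned safety table.

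These harms are central to safety in this trial. Protocol 4.1 names hypotension, renal decline and hyperkalaemia as the focus of dose adjustment, and 6.8 gives each its own subsection. A report built only on reported events would give readers a less complete and less reproducible account of them than the scheduled data allow.

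**Working it through.** **1. Where the values are collected.** Visits 2, 3, 4, 5, 6, 7, 8 and 9 (weeks 1, 2, 4, 5, 14, 26, 39 and 52) make 8 post-baseline visits with urea and electrolytes and with blood pressure. For 100 patients that is at most 8 × 100 = 800 sets of values, before missed visits and the 10% discontinuation that the protocol allows for.

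**2. Where the SAP uses them.**

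- 2.3: baseline table only.
- 2.4.1 to 2.4.3: potassium, creatinine, eGFR and SBP are not named as outcomes, so the repeated-measures biomarker model in 1.7.2 does not name them either. The open-ended biomarker wording in 2.4.3 sits under LV remodelling and neurohormonal levels.
- 2.5.1 withdrawal, 2.5.2 events of interest, 2.5.3 SAEs: no mean, change from baseline, shift table or threshold count for any of the four.
- SBP enters 2.5 once, inside the label for symptomatic hypotension with a systolic value below 90 mmHg. A low reading without symptoms is not counted.

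Protocol 11.3 specifies no laboratory or blood pressure summary.

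**3. What the cross-reference supplies.** Protocol 10.2 gives no numeric criterion for hyperkalaemia, worsening renal function or AKI. It calls the listed items adverse reactions, which Table 10-1 defines by a suspected causal link to the study drug, whereas the SAP calls them adverse events. It does not list cough, which the SAP does. The full details that the SAP promises are therefore not there.

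**4. Sensitivity of the planned comparison.** The documents give no power figure for safety. Their only one is for the primary endpoint, and it reproduces: Φ(6 / (7.8 × √(2/45)) − 1.96) = Φ(3.65 − 1.96) = 95.4%, consistent with the stated figure above 90%. Then 90 / 0.9 = 100 patients, or 50 per arm.

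With 50 per arm and no events in one arm, Fisher's two-sided p-value is twice C(50,k)/C(100,k):

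- 0 versus 5: 2 × 2,118,760 / 75,287,520 = 0.056
- 0 versus 6: 2 × 15,890,700 / 1,192,052,400 = 0.027

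Other smallest splits that reach p < 0.05 are 2 versus 10, 3 versus 11 and 5 versus 14.

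**5. Information lost by counting events only.** This is an illustration, because the documents give no event rates. Assume 50 per arm, two-sided 0.05, one normally distributed value per patient, and an event defined as crossing a fixed limit. The shift that produces rates p1 and p2 is d = z(p2) − z(p1), in SD units. The power for means is Φ(d / √(2/50) − 1.96).

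| Assumed rates | Fisher power | d | Power for means |
|---|---|---|---|
| 5% v 10% | 6% | 0.363 | 44% |
| 5% v 15% | 24% | 0.608 | 86% |
| 10% v 20% | 20% | 0.440 | 60% |

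For 5% v 15%: 0.608 / 0.2 − 1.96 = 1.08, and Φ(1.08) = 86%. The table shows how much the values carry beyond the counts. It is not an argument for adding formal tests.

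**The case against.** The strongest reply is that reporting is less haphazard than it looks. Hyperkalaemia, worsening renal function and AKI are named eCRF items at every follow-up visit. Results are reviewed as they arrive, and potassium above 5.3 mmol/L or an eGFR fall of 25% or more triggers set steps under 6.8. Dose changes are recorded in the eCRF. The trial is double-blind, and nothing in the documents suggests that reporting would differ by arm. The eCRF may also hold event definitions that the reader cannot see. Safety is not an objective or endpoint of this 100-patient mechanistic trial. All of this stands. It limits the harm to lost precision and completeness, and it does not supply the missing definition or summaries.

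A reader might go further and infer that the protocol's limits contradict each other. For example, potassium rising from 5.0 to 5.9 mmol/L is +18% (5.9 / 5.0 = 1.18). It lies above 5.5 in 6.8.2 but does not meet the Appendix 1 entry "Potassium >20% increase, >20% decrease". The documents do not support that inference. The entry limit, the up-titration condition, the management bands and the Appendix 1 percentages serve different purposes, and none is stated to define an adverse event. Protocol 6.8.1 does say "Alert ranges for laboratory and other test abnormalities are included in Appendix 1", but an alert range is not an event definition. A similar argument from creatinine to eGFR would need an equation that the documents do not give.

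A reader might also infer that the values are never analysed or go unused. What can be said is that no analysis is specified: the table shells are not part of these documents, the values guide dosing during the trial, and the TSC reviews safety data periodically.

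**Conclusion.** The point holds as a gap in safety reporting. SAP 2.5.2 tests hyperkalaemia and renal worsening through a cross-reference that gives names without criteria. No post-baseline analysis of potassium, creatinine, eGFR or SBP values is specified in either document, although measurements are scheduled at eight post-baseline visits.

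Its size is modest. The primary endpoint and its analysis are untouched. A bias between arms might be inferred, but blinding argues against it and the documents show none. What can change is the safety conclusion: if events are few, a single report can carry a comparison from p = 0.056 to p = 0.027, and moderate differences in event rates would usually be missed. Few events, and the rates used for power, are assumptions. That the counts depend on reporting is inferred from protocol 10.2 and from the absence of any numeric rule. This is an inexpensive improvement worth making, not a flaw that threatens the trial's main result.

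**What to change.** In SAP 2.5, add for potassium, creatinine, eGFR and SBP:

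- descriptive summaries by arm and visit, with change from baseline;
- the number and percentage of patients ever crossing bands already stated: potassium >5.3, >5.5 and ≥6.0 mmol/L (protocol 6.8.2); eGFR fall from baseline ≥25% and ≥40% (protocol 6.8.1); SBP <90 mmHg regardless of symptoms (the value in SAP 2.5.2).

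Show these beside the reported events. State in 2.5.2 that protocol 10.2 lists the events and does not define them numerically. The bands serve as counting rules only and imply no change to clinical management. Keeping the additions descriptive fits protocol 11.3, which plans safety summaries without formal comparison.

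The cost is a few more safety tables. Laboratory counts may exceed reported-event counts, so a sentence explaining the difference is needed. No new samples are required. Protocol 8.2 is explicit about eCRF entry only for pre-randomisation results. Section 9 makes capture of follow-up values likely, but this should be confirmed before the tables are promised.
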